
 To explore exposure-response relationships between GSK2857916 exposure and clinical endpoints 	
 Explore relationships between GSK2857916 exposure (e.g., dose, dose intensity, concentration, Cmax, or AUC) and clinical endpoints (e.g., response, corneal event), if data permit

 To assess Minimal Residual Disease (MRD) in participants who achieve ≥VGPR or better 	
 Minimal Residual Disease (MRD) negativity rate, defined as: the percentage of participants who are MRD negative by Next Generation Sequencing (NGS).

 To assess the safety, efficacy, immunogenicity, and pharmacokinetics of GSK2857916 in a lyophilized configuration (n = approximately 25 participants) 	
 AEs, clinical and laboratory assessments; Descriptive analyses of ORR, duration of response, time to response, time to progression, overall response; incidence and titers against GSK2857916; plasma concentrations of GSK2857916 (ADC, total mAb, and cys-mcMMAF) and derived pharmacokinetic parameters, if data permit

 Ocular sub-study objective 	

 To evaluate the effect of topical corticosteroids on corneal findings in approximately 30 participants who will receive monocular topical corticosteroids for the first 4 cycles 	
 Description of differences in corneal findings in each eye based on ophthalmic examinations (participant-level).

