2.3. Study Design

Overview of Study Design and Key Features	
	
 • Independent GSK2857916 Lyophilized Configuration Cohort 
 ○ Population: Subjects with relapsed/refractory MM (at least 25 subjects) ○ Objective: To assess the safety, efficacy, immunogenicity, and PK of GSK2857916 in a lyophilized configuration. • Ocular Sub-Study 
 ○ Population: Subjects with relapsed/refractory MM (up to 30 subjects (15 subjects each dose)) ○ Objective: evaluate the effect of topical corticosteroids on corneal findings in subjects who will receive monocular topical corticosteroids for the first 4 cycles and sign an optional ICF.
Dosing	
 • GSK2857916 Frozen Configuration Cohorts 
 ○ GSK2857916 will be administered at a calculated dose of 2.5 mg/kg or 3.4 mg/kg as an IV infusion over at least 30 minutes at the study sites. ○ Independent GSK2857916 Lyophilized Configuration Cohort 
 ○ GSK2857916 will be administered at a calculated dose of 3.4 mg/kg as an IV infusion over at least 30 minutes at the selected study sites when the lyophilized configuration becomes available. ○ Lyophilized configuration cohort will be initiated at 2.5 mg/kg if the results of the IA indicate that 3.4 mg/kg should not be continued. .
Time & Events	
 • Refer to Appendix 2: Schedule of Activities
Treatment Assignment	
 • This is a two-arm, randomized, multi-center, open-label study for GSK2857916 frozen configuration cohort. • For independent lyophilized cohort, there is only one dose group
Interim Analysis	
GSK2857916 Frozen Configuration Cohorts
 
 • One interim analysis (IA) is planned for the primary endpoint ORR after approximately 25 participants per arm are evaluable for response. Further details can be referred to in Section 3 of RAP and Section 4.1 of the protocol (Version: GSK Document Number TMF-13990464).

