 1. Shift table from baseline to worst post-baseline by eye (R/L) and subject (worse eye) for Corneal epithelium (Normal to Abnormal), Corneal ulcer (No to Yes), Microcystic edema (No to Yes), Microcystic without edema (Yes/No), Subepithelial haze (No to Yes), Corneal neovascularization (No to Yes), Stroma (Normal to Abnormal), Active opacity (No to Yes), and Active edema (No to Yes).
 2. For punctate keratopathy, summary table of worst grade and most frequent grade across ocular exams by eye (R/L) and subject (worse eye)
 - ii. Corneal endothelium findings:

1. Shift table from baseline to worst post-baseline by eye (R/L) and subject (worse eye) for Corneal endothelium (Normal to Abnormal)
 2. Summary table by eye (R/L) and subject (either eye) for presence of Descemet's folds and Endothelial lesion at any post-baseline ocular exam.
- j. Pachymetry: Summary table of number (%) of $\geq 5\%$ increase from baseline at worst post-baseline by eye (R/L) and subject (either eye)
- k. Schirmer's Test/ Tear Break-up Time:
- i. Summary table of change from baseline to worst post-baseline by eye (R/L).
 - ii. Shift table from baseline to worst post-baseline by eye (R/L). The categories for Schirmer's Test are ≤ 5 mm, > 5 and ≤ 10 mm, and > 10 mm; the categories for Tear Break-up Time are: ≤ 5 sec, > 5 and ≤ 10 sec, and > 10 sec.
- l. Slit Lamp Exam:
- i. Shift table from baseline to worst post-baseline by eye (R/L) and subject (worse eye) for Anterior Chamber: Deep/Quite (Yes to No); Iris: Flat, round and reactive (Yes to No); and Lens: Clear (Yes to No).
 - ii. Summary tables of presence of iris findings ('Transillumination defect', 'Nodules', or 'Neovascularization') at any post-baseline ocular exam.
 - iii. Shift table from baseline to worst post-baseline by eye (R/L) and subject (worse eye) for Pseudophakia (No to Yes), Nuclear sclerosis (No to Yes), Cortical cataract (No to Yes), and Posterior subcapsular cataract (No to Yes)
 - iv. Summary table of number of subjects (%) underwent surgery due to cataract post-baseline.
- m. FUNDUS Photograph: Shift table from baseline to worst post-baseline by eye (R/L) and subject (worse eye) for Vitreous normal in appearance (Yes to No), PVD (No to Yes), Vitreous cell (No to Yes), Vitreous haze (No to Yes), Optic nerve normal in appearance (Yes to No), and Retina normal in appearance (Yes to No).

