2. General study from EOT visit to last follow-up visit: To assess the change in corneal findings after discontinuation of study treatment, among eyes and subjects (worse eye) with exam finding at EOT visit worse than baseline, the following analyses will be performed.
- a. Summary of change (worsening, no change, improvement) from EOT to last follow-up visit based on categories defined below by eye (R/L) and subject (worse eye)
 - b. Summary of number (%) of eyes and subjects (worse eye) that resolve (improve to baseline level or better based on categories defined below), and descriptive summary of time from EOT visit to resolution among eyes and subjects (worse eye) that resolved

The parameters included in above analyses are:

1. BCVA change from baseline in log MAR scale (< 0.12 , ≥ 0.12 to < 0.3 , ≥ 0.3)
 2. IOP (≥ 22 mm Hg/ <22 mm Hg)
 3. Corneal epithelium (Normal/Abnormal), Punctate Keratopathy (None/Mild /Moderate/Severe), Corneal ulcer (No/Yes), Microcystic edema (No/Yes), Microcystic without edema (No/Yes), Subepithelial haze (No to Yes), Corneal neovascularization (No to Yes), Stroma (Normal/Abnormal); Active opacity (No/Yes); Active edema (No/Yes)
 4. Corneal endothelium (Normal/Abnormal), Descemet's folds (No/Yes; Peripheral/Central), Endothelial lesion (Peripheral/Central)
 5. Pachymetry (increase from baseline $< 5\%$, and $\geq 5\%$), Tear break up time (≤ 5 mm, > 5 and ≤ 10 mm, and > 10 mm), Schirmer's test (≤ 5 sec, > 5 and ≤ 10 sec, and > 10 sec)
3. Ocular sub-study (Cycle 1-4): To evaluate the effect of topical corticosteroids on corneal findings, pending on the availability of data, the following analyses will be performed in up to 30 participants who will receive monocular topical corticosteroids for the first 4 cycles:
- a. Summary of worst grade during Cycle 1-4 of corneal events (GSK scale) in eyes randomized to topical corticosteroids treatment and eyes not.
 - b. BCVA at baseline, at worst during Cycle 1-4, and worst and most frequent category (definite worsen, possible worsen, and no change/improved) of change from baseline during Cycle 1-4 will be summarized in eyes randomized to topical corticosteroids treatment and eyes not. Eyes with a decline in BCVA to 'light perception' (LP) or 'no light perception' (NLP) due to corneal finding anytime post-baseline will also be summarized.

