 - c. Summary of onset time to first study treatment (BCMA)-related corneal finding (GSK scale) in eyes randomized to topical corticosteroids treatment and eyes not.
 - d. Summary of onset time to initiation of topical corticosteroids treatment in eyes randomized to no such treatment.
 - e. Shift in corneal findings (per ocular exam) from baseline to worst during Cycle 1- 4 in eyes randomized to topical corticosteroids treatment and eye not. Corneal findings include Corneal epithelium (Normal to Abnormal), Punctate Keratopathy (None/Mild to Moderate/Severe), Corneal ulcer (No to Yes), Microcystic edema (No to Yes), Microcystic without edema (Yes to No), Subepithelial haze (No to Yes), Corneal neovascularization (No to Yes), Stroma (Normal to Abnormal), Active opacity (No to Yes), and Active edema (No to Yes).

The details of the planned displays are provided in [Appendix 13](#): List of Data Displays.

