Punctate Keratopathy	n	100	100	100	100
	None/Mild to None/Mild	30 (30%)	30 (30%)	30 (30%)	30 (30%)
	None/Mild to Moderate/Severe	50 (50%)	50 (50%)	50 (50%)	50 (50%)
	Moderate/Severe to None/Mild	0	0	0	0
	Moderate/Severe to Moderate/Severe	20 (20%)	20 (20%)	20 (20%)	20 (20%)
Corneal Ulcer	n	100	100	100	100
	Normal to Normal	30 (30%)	30 (30%)	30 (30%)	30 (30%)
	Normal to Abnormal	50 (50%)	50 (50%)	50 (50%)	50 (50%)
	Abnormal to Normal	0	0	0	0
	Abnormal to Abnormal	20 (20%)	20 (20%)	20 (20%)	20 (20%)
Microcystic Edema	n	100	100	100	100
	No to No	30 (30%)	30 (30%)	30 (30%)	30 (30%)
	No to Yes	50 (50%)	50 (50%)	50 (50%)	50 (50%)
	Yes to No	0	0	0	0
	Yes to Yes	20 (20%)	20 (20%)	20 (20%)	20 (20%)

CONFIDENTIAL

205678

Microcystic Without Edema	n	100	100	100	100
	No to No	30 (30%)	30 (30%)	30 (30%)	30 (30%)
	No to Yes	50 (50%)	50 (50%)	50 (50%)	50 (50%)
	Yes to No	0	0	0	0
	Yes to Yes	20 (20%)	20 (20%)	20 (20%)	20 (20%)
Subepithelial Haze	n	100	100	100	100
	No to No	30 (30%)	30 (30%)	30 (30%)	30 (30%)
	No to Yes	50 (50%)	50 (50%)	50 (50%)	50 (50%)
	Yes to No	0	0	0	0
	Yes to Yes	20 (20%)	20 (20%)	20 (20%)	20 (20%)
Corneal Neovascularization	n	100	100	100	100
	No to No	30 (30%)	30 (30%)	30 (30%)	30 (30%)
	No to Yes	50 (50%)	50 (50%)	50 (50%)	50 (50%)
	Yes to No	0	0	0	0
	Yes to Yes	20 (20%)	20 (20%)	20 (20%)	20 (20%)
Stroma	n	100	100	100	100
	Normal to Normal	30 (30%)	30 (30%)	30 (30%)	30 (30%)
	Normal to Abnormal	50 (50%)	50 (50%)	50 (50%)	50 (50%)
	Abnormal to Normal	0	0	0	0
	Abnormal to Abnormal	20 (20%)	20 (20%)	20 (20%)	20 (20%)
Active Opacity	n	100	100	100	100
	No to No	30 (30%)	30 (30%)	30 (30%)	30 (30%)
	No to Yes	50 (50%)	50 (50%)	50 (50%)	50 (50%)
	Yes to No	0	0	0	0
	Yes to Yes	20 (20%)	20 (20%)	20 (20%)	20 (20%)
Active Edema	n	100	100	100	100
	No to No	30 (30%)	30 (30%)	30 (30%)	30 (30%)
	No to Yes	50 (50%)	50 (50%)	50 (50%)	50 (50%)
	Yes to No	0	0	0	0
	Yes to Yes	20 (20%)	20 (20%)	20 (20%)	20 (20%)

Example SAFE_T21
 Protocol: 205678
 Population: Full Safety

Table x.xxxx
 Summary of Blurred Vision (CTCAE) Characteristics II

	2.5 mg/kg (N= xx)	3.4 mg/kg (N= xx)	3.4 mg/kg (N= xx)
Time to onset of first occurrence, days			
n	XX	XX	XX
Mean	XX.X	XX.X	XX.X
SD	XX.XX	XX.XX	XX.XX
Median	XX.X	XX.X	XX.X
Min.	XX	XX	XX
Max.	XX	XX	XX
1 - 21	XX (XX.X%)	XX (XX.X%)	XX (XX.X%)
22 - 42	XX (XX.X%)	XX (XX.X%)	XX (XX.X%)
43 - 63	XX (XX.X%)	XX (XX.X%)	XX (XX.X%)
64 - 105	XX (XX.X%)	XX (XX.X%)	XX (XX.X%)
>105	XX (XX.X%)	XX (XX.X%)	XX (XX.X%)

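### The only ocular sub-study summary of punctate keratopathy by steroid-randomized eye merges four grades into two, so None-to-Mild and Moderate-to-Severe changes count as no shift

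*SAP*

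**What the plan says.** The sub-study gives topical corticosteroid to one eye only. Section 2.3 limits it to "up to 30 subjects (15 subjects each dose". Its endpoint in Section 2.2 is "Description of differences in corneal findings in each eye based on ophthalmic examinations (participant-level", which is descriptive; no test, effect size or power is stated.

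Section 8.5 item 3e plans a shift from baseline to worst during Cycles 1-4, for eyes randomized to corticosteroid and eyes not. For keratopathy the categories are "Punctate Keratopathy (None/Mild to Moderate/Severe". In shell SAFE_T20 (Section 15.14, used for Table 3.1200) the off-diagonal rows are "None/Mild to Moderate/Severe" and "Moderate/Severe to None/Mild"; the other two rows are the no-shift rows.

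Elsewhere the SAP keeps the grades apart:

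- Section 8.5 item 2 (end of treatment to last follow-up) lists "Punctate Keratopathy (None/Mild /Moderate/Severe".
- Section 8.5 item 1, for the general study, asks: "For punctate keratopathy, summary table of worst grade and most frequent grade across ocular exams by eye (R/L) and subject (worse eye". The shell is SAFE_T14, the display Table 3.0860.
- Section 8.2.3 item 9d separates None from Mild at baseline, although it joins Moderate with Severe.

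The sub-study also has item 3a: "Summary of worst grade during Cycle 1-4 of corneal events (GSK scale) in eyes randomized to topical corticosteroids treatment and eyes not" (Table 3.1160, shell SAFE_T16, grades 0 to 4).

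**The concern.** The sub-study asks whether topical corticosteroid changes corneal findings, with one treated and one untreated eye per participant. Among the findings in item 3e, punctate keratopathy is the only one with more than two levels, so it is the only one that loses information in the two-by-two format. If the treated eye stays at None while the untreated eye reaches Mild, or the treated eye stays at Moderate while the other reaches Severe, Table 3.1200 puts both eyes in a no-shift row. With so few participants, a difference of that kind could pass unseen in the table built to look for it.

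**Working it through.** **1. Does another sub-study summary table show the grade by randomized eye?** The sub-study tables in Section 15.13.8 are 3.1160 to 3.1200.

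- Table 3.1160: worst GSK-scale grade. It is by randomized eye, but it combines corneal findings with visual acuity. The first example row of shell SAFE_L2 shows the limit: moderate keratopathy (Grade 2) with edema (Grade 3) gives an overall Grade 3, so the keratopathy grade no longer shows.
- Tables 3.1170, 3.1180 and 3.1190: visual acuity, time to first drug-related corneal event, and time to starting steroid in the other eye. None shows the keratopathy grade.
- Table 3.1200: keratopathy by randomized eye, two levels.
- Outside the sub-study block, Table 3.0860 has separate grades but by right and left eye. Steroid is randomized to left or right (Section 5.1), so it cannot be read as treated against untreated.
- Listing 30.0200 lists findings for each eye and identifies the randomized eye. Its shell, SAFE_L2, distinguishes mild from moderate keratopathy.

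The detail is therefore in a listing and partly in a composite grade, but in no summary table.

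**2. What the cut hides.** Four grades give 6 unordered pairs of unequal grades. Two of them, None-Mild and Moderate-Severe, fall inside one collapsed class: 2/6 = 1/3.

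**3. Share of between-eye differences hidden.** The SAP states no figure to reproduce. The inputs below are assumptions, with the same grade distribution p in both eyes. For independent eyes:

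- P(eyes differ) = 1 − Σp²
- P(differ but same class) = 2(p_None·p_Mild + p_Moderate·p_Severe)
- hidden share = second ÷ first

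Uniform grades: 1 − 4(0.25²) = 0.75; 2(0.0625 + 0.0625) = 0.25; share 0.25/0.75 = 33%.

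Grades at the extremes (45/5/5/45%): 1 − (0.2025 + 0.0025 + 0.0025 + 0.2025) = 0.59; 2(0.0225 + 0.0225) = 0.09; share 0.09/0.59 = 15%.

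Grades piled at the low end (50/35/10/5%): 1 − 0.385 = 0.615; 2(0.175 + 0.005) = 0.36; share 0.36/0.615 = 59%.

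For correlated eyes, a latent bivariate normal model gives:

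| Distribution | corr. 0 | 0.5 | 0.8 | 0.95 |
|---|---|---|---|---|
| Uniform | 33% | 46% | 55% | 61% |
| 45/5/5/45% | 15% | 22% | 31% | 45% |
| 50/35/10/5% | 59% | 62% | 66% | 68% |

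Over nine assumed distributions and these four correlations the range is 15% to 68%. As an example in counts, uniform grades with correlation 0.8 give about 13.7 of 30 pairs that differ on four levels, of which about 0.55 × 13.7 = 7.5 are hidden.

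**4. Cell sizes.** SAFE_T20 splits by dose and by eye group: 30/2 = 15 participants per dose, so at most 15 eyes per column.

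**The case against.** The cut is not arbitrary. In SAFE_L2 mild keratopathy is Grade 1 and moderate is Grade 2, and Section 8.2.3 uses that boundary repeatedly: resolution means Grade 1 or better, and the risk-factor model is for Grade 2 or above. All ten findings in SAFE_T20 share one format, and a four-by-four shift has 16 cells for at most 15 eyes. Listing 30.0200 can be read participant by participant with so few people. Table 3.1200 is also tagged for the primary analysis only, and this SAP version describes some primary-analysis work in the past tense, so a change may mean a supplementary output.

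Most of this stands. It justifies keeping the collapsed rows and rating the point as minor. It does not explain why the grades kept elsewhere in Section 8.5 are dropped from the summary by randomized eye.

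Four stronger readings are tempting and are not supported:

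- That a fixed share, such as half, of the between-eye differences is lost. Half lies within the range above, but the SAP has no data from which to choose it.
- That the differences become invisible. The listing retains them.
- That the sub-study loses power. No test is planned, and SAFE_T20 shows counts for each eye group without pairing the eyes.
- That the general study already has a four-level baseline-to-worst shift table for this finding. It does not: item 1 gives worst and most frequent grade, and item 2 reports worsening, no change, improvement and resolution.

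**Conclusion.** The point holds as a presentation weakness with a cheap remedy. Item 3e and SAFE_T20 record None-to-Mild and Moderate-to-Severe changes as no shift in the only sub-study summary table of keratopathy by steroid-randomized eye. The two hidden pairs out of six follow from the categories alone. Any percentage of eye pairs affected depends on an assumed grade distribution, an assumed between-eye correlation and, in the model used here, equal distributions in the two eyes: 33% for uniform independent grades, about 15% to 68% over the scenarios tried. It affects a descriptive exploratory table and no inference.

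**What to change.** In item 3e and SAFE_T20:

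- Show punctate keratopathy as None, Mild, Moderate and Severe at baseline and at worst during Cycles 1-4, for treated and untreated eyes. A baseline-by-worst shift shows each change; if that is too sparse, the SAFE_T16 layout (baseline rows, then worst rows) at least shows the net movement.
- Keep the existing None/Mild against Moderate/Severe shift as a summary below it.
- Preferably add a within-participant cross-tabulation of worst grade in the treated eye against the untreated eye. Four grades in the present layout would still show the two eye groups separately, whereas the endpoint in Section 2.2 is at participant level.

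The grades are already used at this level elsewhere in the SAP, so no new data are needed. The cost is one shell and one table, longer and with small cells, possibly as a supplementary run if the primary-analysis output already exists.

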	Change from Baseline	n	xx	xx	xx
		Mean	x.x	x.x	x.x
		SD	x.xx	x.xx	x.xx
		Median	x.x	x.x	x.x
		Min	x.x	x.x	x.x
		Max	xx.x	xx.x	xx.x

[figure not shown]
Example: PRO_F1
Protocol: 205678
Population: Safety

Page 1 of 1
(Data as of: 30MAY2001)

Figure x.xxxx

Stacked Bar Chart of PRO-CTCAE Score by Attributes and Visit

Item X

Programming note: There is flexibility in choosing colour.

Example SAFE_L2
 Protocol: 205678
 Population: Safety

Page 1 of 1
 (Data as of: 24APR2018)

Listing X
 Listing of Corneal Findings (GSK Scale)

Treatment Group A

Centre Id/ Subj.	Age (y) / Sex/ Race	Eye	Grade/ Exam Finding(s)	Overall Grade of Corneal Examination Findings/Visual Acuity Grade/Overall Grade for GSK Scale for this eye	Date of Assessment /Visit	Time Since 1st Dose/ Last Dose	Action(s) Taken with study treatment/ Related
PPD [redacted]	PPD [redacted]	Left	Grade 2/ Moderate keratopathy, Grade 3/Diffuse Epithelial or stromal edema	Grade 3/ Not Applicable/ Grade 3	PPD [redacted] / Week 4	15 d/ 10 d	Dose reduced, Dose interrupted/delaye d/ No
		Right	Grade 3/ Diffuse microcysts	Grade 3/ Grade 1/ Grade 3	PPD [redacted] / Week 4	30 d/ 0 d	Dose interrupted/delaye d/ Yes
		Left	Grade 1/Mild superficial keratopathy	Grade 1/ Not Applicable/ Grade 1	PPD [redacted] / Week 7	32 d/ 0 d	Dose interrupted/delaye d / No
		Right	Grade 1/Mild superficial keratopathy	Grade 1/ Not Applicable/ Grade 1	PPD [redacted] / Week 7	32 d/ 0 d	Dose interrupted/delaye d /No

Treatment Group B

 Treatment Group C

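### SAP Section 8.5 item 3e prints the shift for microcysts without edema in the reverse direction, and no shell or programming note says which value is worst

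*SAP*

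**What the plan says.** Section 8.5 names this finding in three analyses and writes it three ways.

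- Item 3e (ocular sub-study, Table 3.1200) is introduced as "Shift in corneal findings (per ocular exam) from baseline to worst during Cycle 1- 4 in eyes randomized to topical corticosteroids treatment and eye not". Its list includes "Microcystic without edema (Yes to No), Subepithelial haze (No to Yes".
- Item 1, corneal epithelium findings (general study, baseline to worst post-baseline, Table 3.0851), has "Microcystic without edema (Yes/No", a pair with no direction.
- Item 2 (end of treatment to last follow-up) has "Microcystic without edema (No/Yes".

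In Section 15.13.8, Table 3.1200 points to shell SAFE_T20 and Table 3.0851 to shell SAFE_T9. The programming-note cell is empty for both. For this finding SAFE_T20 prints all four transitions between No and Yes. SAFE_T9 prints generic categories. The mock listing SAFE_L2 shows "Diffuse microcysts" as an example of a Grade 3 exam finding.

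**The concern.** A baseline-to-worst shift collapses several exams per eye into one value, so the programmer must know which category is worse. In the shift analyses of Section 8.5 that information sits in the bracket after each finding. For microcysts without edema, the bracket in item 3e points from present to absent. Read as the other brackets are read, it makes absence the worse state.

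The sub-study endpoint in Section 2.2 is a description of how corneal findings differ between a participant's two eyes, one treated with topical steroid and one not. Table 3.1200 is the display that shows this for individual exam findings. If the direction were taken literally, microcysts that come and go would drop out of the between-eye description for this finding.

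**Working it through.** The plan gives no figure to reproduce here. The check sets the passages side by side and then counts what a literal coding would do.

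**Step 1: the convention.** In the shift analyses of items 1 and 3e, directional pairs run from better to worse. Ulcer, microcystic edema, haze, neovascularization, active opacity and active edema go from No to Yes. Epithelium and stroma go from Normal to Abnormal. Punctate keratopathy in item 3e goes from None/Mild to Moderate/Severe. Elsewhere in item 1, Yes to No appears only where Yes is the healthy state, for example full muscle movement, a clear lens or a normal-looking retina. Microcysts without edema in item 3e is the only abnormal sign given as Yes to No.

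**Step 2: the neighbouring text.** Within item 3e the entry stands directly after its sibling, which has the opposite direction. In item 1 the surrounding list reads "Microcystic edema (No to Yes), Microcystic without edema (Yes/No), Subepithelial haze (No to Yes", so this is the one finding there without a direction. Item 1 also asks for a worse-eye summary, which needs the same ordering. In item 2 the text reads "Microcystic edema (No/Yes), Microcystic without edema (No/Yes), Subepithelial haze (No to Yes".

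**Step 3: can the shells settle it?** SAFE_T20 has a row for each of the four transitions, but a row label does not say how the worst exam is chosen. Its dummy percentages (30, 50, 0, 20) repeat for every finding and are placeholders. The shell also departs from the text for corneal ulcer, using Normal/Abnormal where item 3e uses No/Yes, so it is not a reliable tie-breaker.

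**Step 4: consequence of literal coding.** Take an eye with No at baseline, k post-baseline exams in Cycles 1-4, and Yes at one or more of them. There are 2^k − 1 such exam patterns.

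- If No is the worse value, any clean exam makes the worst value No. Only the all-Yes pattern stays No to Yes, so 2^k − 2 patterns become No to No.
- If Yes is the worse value, all 2^k − 1 patterns are No to Yes and none is lost.

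The number of exams is an assumption, because the visit schedule is in the protocol. The programming note for Table 3.0340 mentions sub-study visits on Day 1 and Day 10 of Cycles 1-4, which is 4 × 2 = 8. Section 5.2 takes a Day 1 assessment without a recorded time as baseline, which leaves 8 − 1 = 7. Section 15.5.2 admits unscheduled visits to worst-case analyses. A range is therefore shown.

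| k | Patterns with at least one Yes | Shown as No to No, literal coding | Shown as No to No, presence as worst |
|---|---|---|---|
| 1 | 1 | 0 | 0 |
| 2 | 3 | 2 | 0 |
| 4 | 15 | 14 | 0 |
| 7 | 127 | 126 | 0 |
| 8 | 255 | 254 | 0 |

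These are counts of possible patterns, not probabilities. By the same logic, a baseline-Yes eye that is clear at one exam would be shown as Yes to No even if microcysts returned.

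**The case against.** The strongest reply is that this is a slip of the pen. No sentence in the SAP defines worst as absence of microcysts, and a programmer would have to treat the absence of a corneal toxicity finding as its worst state. The bracket notation is also loose elsewhere: item 2 mixes slash pairs with directional pairs, and the ulcer labels differ between text and shell. All of this stands, and it makes any misclassification conditional on literal coding.

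Three stronger readings are tempting, and the document does not support them.

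- A reader might infer that the SAP sets worst to mean absent. That is an inference from one bracket.
- A reader might infer that new microcysts would go down as no finding. What is recorded does not change; only the summary in one row might. Even on the literal reading an eye with microcysts at every exam appears as No to Yes. Table 3.1160 (worst GSK-scale grade by randomized eye), Table 3.1180 (onset of the first drug-related event) and Listing 30.0200 do not use this bracket.
- A reader might infer that eight exams are at stake and that the eyes lost are exactly those with onset after the first exam. Section 5.2 can make Cycle 1 Day 1 the baseline. Eyes with onset at the first exam and later clearance would be affected too, so the sets differ.

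The SAFE_L2 entry is weak support: it is an illustrative row and does not say that edema was absent. The reversal is shown by the convention in Section 8.5 without it.

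What the reply does not remove is that the reversed bracket sits in the specification of a derivation, and that no shell or programming note overrides it.

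**Conclusion.** The direction in item 3e is reversed. It conflicts with its own list and is inconsistent with item 2, while item 1 leaves the direction open. If it is coded literally, baseline-No eyes with microcysts at some but not all post-baseline exams in Cycles 1-4 are shown as No to No in Table 3.1200. Whether it was coded that way cannot be told from the SAP.

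The reach is small. It is one descriptive row of one sub-study table, in up to 30 participants and dependent on data availability, with no test or decision rule attached. Table 3.0851 is exposed only to an unstated direction, not a reversed one. The primary endpoint and type I error are not affected. The point is still worth acting on, because the row compares steroid-treated with untreated eyes and, with so few eyes, a handful misclassified could change the description.

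**What to change.** - In Section 8.5 item 3e, change the direction for microcysts without edema to No to Yes.
- In Section 8.5 item 1, corneal epithelium findings, give the same finding the direction No to Yes.
- State in the text, or in the programming notes for Tables 3.1200 and 3.0851, that worst means present at any post-baseline exam in the analysis window: Cycles 1-4 for Table 3.1200, and any post-baseline exam for Table 3.0851.
- Check the worst-value coding of both tables. Table 3.1200 belongs to the primary-analysis delivery only (SAC [1]), so the check may concern output already produced. Table 3.0851 is also due at end of study (SAC [2]).

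The cost is a few words of SAP text and a programming check. If the check finds literal coding, the affected row of Table 3.1200 needs to be rerun. No data collection, sample size or other analysis changes.
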